4.3.2.3 Incidence of TEAEs by Severity

The number and percentage of patients reporting a TEAE will be tabulated by investigator-specified severity, i.e. intensity of mild, moderate or severe. A patient experiencing AEs of the same SOC and PT multiple times during the study will be counted once for the PT based on the worst severity reported. Similarly, if a patient experiences multiple AEs within the same SOC, the patient will be counted once for that SOC at the worst severity reported.

Missing severity for an event will be assigned to severe.

4.3.2.4 Incidence of TEAEs by Relationship to Study Drug

The number and percentage of patients reporting a TEAE will be summarized by SOC, PT, and relationship to study drug (related or not related). A patient experiencing AEs of the same SOC and PT multiple times during the study will be counted once for the PT based on the highest level of relatedness reported (related > not related). Similarly, if a patient experiences multiple AEs within the same SOC, the patient will be counted once for that SOC at the highest level of relatedness reported.

Events missing relationship will be summarized as related to study drug if the AE occurs on or after the administration of study drug.

4.3.2.5 Serious Adverse Events (SAEs)

The number and percentage of patients reporting at least one AE that meets with criteria for an SAE will be summarized by MedDRA SOC and PT. A similar summary of SAEs reported as related to study drug will be presented. The seriousness reason will be provided in the by-patient SAE listing.

4.3.2.6 AEs Leading to Study Discontinuation

A listing of any AEs reported as leading to study discontinuation will be presented as described in Section 4.3.2.2 above.

4.3.2.7 AEs Leading to Death

All deaths occurring during the study, including AEs leading to death and deaths during the post-treatment follow-up period, will be listed.

4.3.3 Clinical Laboratory Tests

Laboratory data collected in this study include serum chemistry and hematology values, urinalysis results and [REDACTED] levels. The baseline laboratory value is defined as the last value observed prior to the first administration of study drug. Any values collected after the administration of study drug are regarded as post-baseline. Change from baseline will be calculated as the post-baseline value minus the baseline value. Only the

numeric part in laboratory values that contain non-numeric qualifiers, such as less than (<) a certain value or greater than (>) a certain value, will be used in the summary statistics.

Laboratory values and change from baseline in these values will be listed and summarized for patients in the Safety Population by group (chemistry, hematology or urinalysis) and by visit. [REDACTED] will be presented separately by visit. Listings of patients with positive drug screen or pregnancy results will be provided.

Descriptive summaries of continuous laboratory values and change from baseline in these values will include the number of observations, mean, SD, median, minimum and maximum values at each time point. Data will be summarized in SI units. Shift tables comparing baseline classification based on reference range (i.e., normal, low, or high) to the worst classification recorded post-baseline will be presented. In the case that a patient has both “low” and “high” post-baseline results for the same laboratory parameter, the patient will be counted under both “low” and “high”. A patient will be counted under the “normal” category post-baseline only if all post-baseline results are categorized as “normal”.

For non-numeric urinalysis data, a shift table comparing baseline results (negative, trace or positive) to the maximum post-baseline result will be presented.

Listings of laboratory results for each patient will be presented. Values outside of the laboratory’s reference range will be flagged in the listing. A by-patient listing of laboratory values outside the normal reference range for the parameter will be produced.

4.3.4 Vital Signs and Physical, Neurological and Developmental Examination Findings

4.3.4.1 Vital Signs

Vital signs measured in this study include systolic and diastolic blood pressure, heart rate, respiratory rate, and body temperature. Baseline for vital signs will be the values obtained at the last assessment prior to the first dose of IP, typically Visit 2, Day 0. Change from baseline is calculated as the post-baseline value minus the baseline value. Missing values will not be imputed.

Absolute values and changes from baseline in vital signs at each visit will be summarized for Parts A and B and overall in the Safety Population using descriptive statistics (n, mean, SD, median, minimum, and maximum). A by-patient, by-visit listing of vital signs collected and height and weight recorded will be provided.

All vital signs included the parameter values and overall interpretations will be listed. Changes from baseline physical examination findings will also be listed individually by patient.

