7.7.7. Tanner Staging

The Tanner scale (also known as the Tanner stages) is a scale of physical development in children, adolescents and adults. The scale defines physical measurements of development based on external primary and secondary sex characteristics. Patients will be evaluated and rated as Tanner I, Tanner II, Tanner III, Tanner IV, and Tanner V. Tanner staging will occur at Visit 1 (screening) and Visit 5a (only for patients who do not continue into Part B) of the treatment period (Part A), and at the Final OLE Visit or Taper Visit (Part B).

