9.7. Safety Analyses

Safety will be reported for all patients. The results in Part A and Part B will be summarized separately and then the combined results in Part A and Part B will be summarized together. Adverse events will be tabulated by overall, system organ class, and Preferred Term using the Medical Dictionary for Regulatory Activities (MedDRA) coding system. Incidence and percentage of AEs will be presented. Additional tables, with AEs classified by severity and by only those related to drug as assessed by the investigator will be presented. Subset listings will be produced for AEs that cause withdrawal and for SAEs. Clinical laboratory tests (hematology, chemistry and urinalysis), vital signs (temperature, BP, pulse rate), weight, and ECGs will be summarized using descriptive statistics including changes from baseline. Change in C-SSRS scores where applicable will be determined. Physical, neurological and developmental examinations will be summarized using number and percentage of patients with abnormalities.

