4.3.4.4 Developmental Examination Findings

Developmental examinations will be conducted on pediatric patients 2 to 17 years of age, inclusive. Developmental parameters assessed include speech and language skills, motor skills and social skills with findings recorded as normal, abnormal but not clinically significant, and abnormal and clinically significant. The number and percentage of pediatric patients with abnormal developmental findings will be summarized by parameter. Abnormal developmental findings at baseline and any changes in neurological findings at post-baseline visits relative to the previous visit will be listed for each patient.

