4.3.6.2 Tanner Scale

The Tanner scale is a scale of physical development in children, adolescent and adults. Patients will be rated as Tanner I, Tanner II, Tanner III, Tanner IV or Tanner V at baseline and end of Parts A and B of the study. The number and percentage of patients in each category will be summarized and listed by visit.

Confidential

[REDACTED]

[REDACTED]

[REDACTED]

[REDACTED]

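### No table specified in the SAP shows within-patient change in weight or in Tanner stage, although the protocol asks for weight change and Tanner is staged in different patients after screening

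*SAP*

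**What the plan says.** **Weight.** Protocol 9.7 states that "vital signs (temperature, BP, pulse rate), weight, and ECGs will be summarized using descriptive statistics including changes from baseline". SAP 4.3.4.1 opens with its own list: "Vital signs measured in this study include systolic and diastolic blood pressure, heart rate, respiratory rate, and body temperature". Its summary rule is that "Absolute values and changes from baseline in vital signs at each visit will be summarized for Parts A and B and overall". Height and weight come in only with the next output: "A by-patient, by-visit listing of vital signs collected and height and weight recorded will be provided". SAP 1.2.4, the list of safety endpoints, puts height and weight inside the vital signs. SAP 4.1.3 summarises weight as a baseline characteristic, without change. SAP section 6 declares no change to the planned analyses.

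**Tanner stage.** Protocol 7.7.7 stages patients at Visit 1, at "Visit 5a (only for patients who do not continue into Part B) of the treatment period (Part A", and at the final extension or taper visit in Part B. The schedules in both documents agree. SAP 4.3.6.2 says instead that patients are rated at baseline and when each part ends. Its analysis is: "The number and percentage of patients in each category will be summarized and listed by visit".

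**Developmental examination.** SAP 4.3.4.4 tabulates the number and percentage of patients aged 2 to 17 with abnormal developmental findings. It then says that "any changes in neurological findings at post-baseline visits relative to the previous visit will be listed for each patient".

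**The concern.** Enrolment starts at age 2, the extension runs at least to Week 36 on the schedule, and long-term safety is a secondary objective. Weight and pubertal stage are the two repeated measures most directly tied to physical development. For both, the useful quantity is the change in the same patient, and the SAP text specifies no table of it.

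The protocol's background gives some reason to look. In its fragile X trial in ages 5 to 17, vomiting and decreased appetite were each reported in 8 of 59 ganaxolone patients (13.6%). That shows relevance only. Placebo rates for these two events are not given there, and in the controlled period of the infantile spasms study vomiting was 11% in both groups.

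**Working it through.** The documents give no figure to reproduce here. The check sets the texts side by side, with one arithmetic illustration.

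**Weight**

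| Source | Is weight a vital sign? | Output for weight |
|---|---|---|
| Protocol 9.7 | Named separately | Summary with change from baseline |
| SAP 1.2.4 | Yes | None stated (endpoint list) |
| SAP 4.1.3 | Not stated | Baseline summary only |
| SAP 4.3.4.1 | Not in its list; named in addition to vital signs | Listing by patient and visit |

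Read with SAP 1.2.4, the summary rule in 4.3.4.1 could cover weight. Read by its own list, and by a listing sentence that adds weight to the vital signs, it does not. The data exist: weight is scheduled at Visits 1 to 8.

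**Tanner: who is staged**

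- Visit 1: all patients.
- Visit 5a: only those not entering Part B.
- Final extension or taper visit: only Part B patients.

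The two later groups are disjoint, and Visit 1 is their union. Patients scheduled at both post-baseline visits: 0.

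**Tanner: what the by-visit table can show when no patient changes stage**

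Let N = 30 (planned enrolment), k = number entering Part B, and pc and pn = share at stage I–II among those who do and do not enter. The values of k, pc and pn are assumptions, and everyone due is taken to be staged.

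- Screening share = [k·pc + (N − k)·pn] / N
- Visit 5a share = pn, so its difference from screening is (k/N)(pn − pc)
- Final visit share = pc, so its difference from screening is ((N − k)/N)(pc − pn)

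| k | pc, pn | Screening | Visit 5a | Final visit |
|---|---|---|---|---|
| 20 | 60%, 30% | (12+3)/30 = 50% | 3/10 = 30% | 12/20 = 60% |
| 20 | 30%, 60% | (6+6)/30 = 40% | 6/10 = 60% | 6/20 = 30% |
| 10 | 60%, 30% | (6+6)/30 = 40% | 6/20 = 30% | 6/10 = 60% |
| 10 | 30%, 60% | (3+12)/30 = 50% | 12/20 = 60% | 3/10 = 30% |
| 20 | 50%, 50% | 15/30 = 50% | 5/10 = 50% | 10/20 = 50% |

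For the first row, (20/30)(0.30 − 0.60) = −0.20 and (10/30)(0.60 − 0.30) = +0.10, which match the table. Across the rows with unequal mix, each later column differs from screening by 10 to 20 points, in either direction. With equal mix the difference is 0.

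**Developmental.** SAP 4.3.4.3 already lists changes in neurological findings. The same word in 4.3.4.4 looks like a carry-over, and it leaves that section without a listing of developmental changes.

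**The case against.** A reader might infer that growth and development effects in children cannot be read from this plan at all. The documents do not support that. SAP 2.1 lists all assessments by study part, patient and visit; weight and Tanner have their own listings; abnormal developmental findings are tabulated; and any adverse event of weight or appetite goes into the event tables. With about 30 patients, listings can be worked through.

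A reader might also infer that the SAP plainly removed the weight summary. That is too strong: SAP 1.2.4 supports a reading that includes weight. The SAP also cites Version 2 of 12 May 2020, while the protocol supplied is dated 11 Jun 2021, so the text the SAP followed cannot be checked. Nor is every Tanner column a separate group, since screening contains everyone.

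Further, the protocol prescribes no Tanner analysis, and its schedule, not the SAP, creates the uneven staging. The Tanner shares above are assumed. The developmental point is a wording slip. Height growth is limited mainly by collection: Protocol 7.7.3 takes height at screening only, although 7.3.1 also names it at Visit 5.

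All of this stands, and it sets the size of the point. It does not supply a weight-change table, because 4.3.4.1 is the section a programmer follows. Nor does it make the Tanner percentages comparable across visits.

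**Conclusion.** The point holds in a limited form. On the readable SAP text, no specified table shows within-patient change in weight or Tanner stage. For weight, the SAP conflicts with itself, and 4.3.4.1 as written falls short of the supplied Protocol 9.7 with no departure declared. For Tanner, the post-baseline percentages can differ from screening purely because of who is staged: 10 to 20 points under the assumed inputs, none if leavers and continuers have the same stage mix. The developmental item is a minor correction.

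The conclusion assumes that the schedule is followed and that neither the separate table templates (SAP section 8, not supplied) nor the blacked-out SAP text already contains these tables. The consequence is that changes are harder to see and must be worked out from listings. Without a control group, the added tables would describe change, not attribute it to treatment.

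**What to change.** 1. **SAP 1.2.4 and 4.3.4.1.** Make the two definitions of vital signs agree. Add weight and change from baseline by visit for Part A, Part B and overall, shown for the age groups that SAP 4.1.3 already defines (17 or under, over 17). Otherwise expected growth in children is pooled with adults. Because SAP 2.5 plans no subgroup analyses, say that this is a display of a safety table; SAP 4.3.6.1 already separates adult and paediatric suicidality data in the same way.
2. **SAP 4.3.6.2.** Correct the timing to match Protocol 7.7.7. Add a shift table from screening to each patient's last Tanner rating, in patients aged 17 or under. SAP 4.3.3 already uses baseline-to-post-baseline shift tables for laboratory data. A footnote should say that the interval differs by group: on the schedule, 20 weeks for Part A completers who leave (Week −4 to Week 16) and 40 weeks for those staged at Week 36.
3. **SAP 4.3.4.4.** In the change listing, replace *neurological* with *developmental*.

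The cost is SAP wording and two extra tables from data already collected. No visit or assessment is added.

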4.3.4.2 Physical Examination Findings

Physical examinations will be conducted at all clinic visits and findings will be recorded as normal, abnormal but not clinically significant, and abnormal and clinically significant. Abnormal changes in baseline physical examinations findings will be summarized using counts and percentages of patients in the Safety Population. Abnormal findings noted at baseline will be listed for each patient. Any changes in physical examination findings at post-baseline visits relative to the previous visit will be listed.

4.3.4.3 Neurological Examination Findings

Neurological examinations will be conducted at all clinic visits and will include evaluation of cranial nerves, motor function, sensory function, reflexes and coordination/cerebellar function. Findings will be recorded as normal, abnormal but not clinically significant, and abnormal and clinically significant. The number and percentage of patients with abnormal neurological findings will be summarized by parameter. Abnormal neurological findings at baseline will be listed for each patient. Any changes in neurological findings at post-baseline visits relative to the previous visit will be listed.

4.3.4.4 Developmental Examination Findings

Developmental examinations will be conducted on pediatric patients 2 to 17 years of age, inclusive. Developmental parameters assessed include speech and language skills, motor skills and social skills with findings recorded as normal, abnormal but not clinically significant, and abnormal and clinically significant. The number and percentage of pediatric patients with abnormal developmental findings will be summarized by parameter. Abnormal developmental findings at baseline and any changes in neurological findings at post-baseline visits relative to the previous visit will be listed for each patient.

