2 STATISTICAL CONSIDERATIONS

2.1 GENERAL CONSIDERATIONS

Statistical analyses will be performed using SAS System, Version 9.4 or higher (SAS Institute, Inc., Cary, NC).

No formal hypothesis testing will be performed for this study. Data will be summarized descriptively. Separate summaries will be presented for data collected in Part A and data collected in Part B of the study. Unless otherwise specified, descriptive statistics for continuous variables will include number of non-missing observations (n), arithmetic mean, standard deviation (SD), 25th and 75th percentiles, minimum, median and maximum. For categorical variables, descriptive statistics including counts and percentages will be used. Only observed data will be summarized. Missing data will not

be imputed. Scheduled assessments will be included in summaries with the exception of reports of abnormal laboratory, vital sign, or ECG values.

Study data from all assessments (scheduled and unscheduled) will be displayed in individual data listings by study part (Part A or Part B), patient and visit, if applicable.

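### Neurological and developmental examinations are tabulated only as percentage abnormal, so no planned table shows within-patient change, and the developmental section's change listing names neurological findings instead

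*SAP*

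**What the plan says.** For neurology, SAP 4.3.4.3 plans one table: "The number and percentage of patients with abnormal neurological findings will be summarized by parameter". It also lists baseline abnormalities, and adds: "Any changes in neurological findings at post-baseline visits relative to the previous visit will be listed".

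For development, SAP 4.3.4.4 plans the same kind of table: "The number and percentage of pediatric patients with abnormal developmental findings will be summarized by parameter". Baseline developmental abnormalities are listed. The sentence on later visits then reads "any changes in neurological findings at post-baseline visits relative to the previous visit will be listed for each patient", so the word is *neurological* in a section about developmental findings.

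Both sections record each finding as normal, abnormal but not clinically significant (NCS), or abnormal and clinically significant (CS).

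Other safety data are handled differently. For physical examinations (SAP 4.3.4.2): "Abnormal changes in baseline physical examinations findings will be summarized using counts and percentages of patients in the Safety Population". For laboratory data (SAP 4.3.3) the plan includes "Shift tables comparing baseline classification based on reference range" with the worst post-baseline classification. Vital signs (4.3.4.1) and ECG (4.3.5) are summarised with change from baseline.

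Protocol 9.7 plans only the number and percentage with abnormalities for all three examinations.

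**The concern.** Neurological and developmental findings are named safety endpoints for Parts A and B (SAP 1.2.4), and preliminary safety is part of the primary objective (SAP 1.1.1). The population has seizures uncontrolled on two or more drugs, and the SAP collects intellectual disability as a baseline characteristic (4.1.3). Some patients can therefore be expected to have abnormal examinations before the first dose.

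In that setting a percentage abnormal mixes deficits present at entry with changes on treatment. The useful safety question is whether a patient's own rating got worse, and the planned tables do not answer it. For development, the sentence that should provide a listing of changes names the wrong examination.

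**Working it through.** The plan states no figure to reproduce. The check compares the sections and then works out what the planned count can register.

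**1. What each section provides**

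| Examination | Table | Dedicated change listing |
|---|---|---|
| Physical (4.3.4.2) | Abnormal changes, n (%) | Yes, against previous visit |
| Neurological (4.3.4.3) | n (%) abnormal by parameter | Yes, against previous visit |
| Developmental (4.3.4.4) | n (%) abnormal by parameter | None as worded |

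**2. What the count can register**

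Take one parameter, n patients rated at baseline and at one later visit. Let A be the number abnormal at baseline, a the number newly abnormal, b the number resolved to normal, and c the number moving from NCS to CS.

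- Percentage abnormal at baseline: 100 × A / n
- Percentage abnormal at the later visit: 100 × (A + a − b) / n
- Difference: 100 × (a − b) / n

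The term c does not appear, and a and b enter only through their difference.

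**3. Illustration with assumed counts (not from the documents)**

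Ten children, eight abnormal on one parameter at baseline: 8 / 10 = 80%.

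- Four of the eight move from NCS to CS (a = 0, b = 0, c = 4): (8 + 0 − 0) / 10 = 80%. The table shows no difference, although four children worsened.
- One child becomes abnormal and another resolves (a = 1, b = 1, c = 0): (8 + 1 − 1) / 10 = 80%. Again no difference, although one child worsened.

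A three-level shift table would put four children in the NCS-to-CS cell in the first case and one in a normal-to-abnormal cell in the second.

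**4. What remains visible elsewhere**

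- SAP 2.1: "Study data from all assessments (scheduled and unscheduled) will be displayed in individual data listings by study part", and also by patient and visit where applicable. A change of category can be read there by hand.
- SAP 3.2: safety summaries are by actual visit, so the percentages can be compared across visits. They are still marginal percentages and are masked as in step 3.
- SAP 4.3.4.3: neurological visit-to-visit changes are listed. With the baseline listing, they give each patient's path from baseline.
- Protocol 8.1.1: a pretreatment event that worsens after treatment starts is recorded as a new adverse event, which then enters the treatment-emergent tables.

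**The case against.** The strongest reply is that the information is not lost. A reader of SAP 4.3.4.4 might infer that no planned output shows developmental worsening. The documents do not support that: the general listings in SAP 2.1, the by-visit summaries in SAP 3.2 and the adverse event rule in Protocol 8.1.1 all bear on it. The common CNS effects named in Protocol 1.2 (somnolence, dizziness, fatigue) would appear in the adverse event tables in any case.

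Other parts of the reply also stand.

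- The SAP follows Protocol 9.7, so the two documents do not conflict.
- Comparison with the previous visit is also used for the physical examination listing, and for neurology it loses nothing once combined with the baseline listing.
- Table and listing templates are in a separate document (SAP 8) that is not available here, so the wrong word may not reach the outputs.
- Scheduled examinations do not extend through the whole of Part B. After Visit 8, assessments are at the investigator's discretion (Protocol 7.3.5).
- In a single-arm study, no shift table can separate a drug effect from the course of the disease.

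The reply does not cover the tables. Reconstructing change from raw listings by patient, parameter and visit is not a summary. The adverse event route depends on investigator judgement: SAP 4.3.5 says that clinically significant ECG abnormalities are also reported as adverse events, but 4.3.4.3 and 4.3.4.4 say nothing similar, and Protocol 8.1.5 names laboratory, vital sign and ECG changes without naming examination findings.

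**Conclusion.** The point holds as a low-severity reporting gap. No planned table for either examination, and no dedicated listing for the developmental one, isolates within-patient change. Worsening within the abnormal range never alters the tabulated percentage, and new abnormalities show only net of resolutions. This follows from the SAP's three-level rating and two-level summary and needs no assumption about rates. The word *neurological* in 4.3.4.4 is a plain drafting slip.

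No count of affected patients can be given. A reader might try to derive one from the 30 planned patients and the rate of about 50% for attention deficit hyperactivity disorder and autism in the Protocol's rationale. That does not work, for three reasons:

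- Those are behavioural diagnoses, not examination abnormality rates.
- The summaries are by parameter, so a child abnormal in speech can still register a new motor abnormality.
- Developmental examinations cover ages 2 to 17 only, in a trial enrolling ages 2 to 65, and the number of children is not stated.

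Sample size and the primary efficacy endpoint are unaffected.

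**What to change.** 1. In SAP 4.3.4.3 and 4.3.4.4, add a shift table by parameter from baseline (normal / abnormal NCS / abnormal CS) to worst post-baseline rating, for Part A, Part B and overall. Use children aged 2 to 17 as the developmental denominator.
2. In SAP 4.3.4.4, change *neurological findings* to *developmental findings* in the listing sentence, and check that the listing template agrees.
3. Optionally, list changes against baseline as well as against the previous visit. This is a convenience, because the baseline listing plus visit-to-visit changes already gives the path.

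The cost is a few lines of SAP text and an adaptation of the laboratory shift-table layout in SAP 4.3.3. The ratings are already collected, so no new data or visits are needed.
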